13.2 Biomarker Analyses

For biomarkers the observed values, the absolute and percent change from baseline will be summarized by nominal time point by descriptive statistics (n, mean, SD, %CV, minimum, Q1, median, Q3, maximum, geometric mean, geometric %CV). The MMRM as described for FXIIa-mediated kallikrein activity is also applicable for all biomarkers and aPTT (absolute change from baseline for each).

Individual observed biomarker time profiles will be plotted using actual sampling times. Mean (\pm SD) observed biomarker time profiles will be plotted by using nominal (planned) time points.

Biomarker: C-C motif chemokine ligand 18 (CCL-18), plasminogen activator inhibitor 1 (PAI-1), surfactant protein A (SP-A), surfactant protein D (SP-D), YKL-40, released N

terminal pro-peptide of type III collagen (PROC3), C terminal of released C5 domain of type VI collagen (PROC6), neo-epitope of MMP-9 mediated degradation of type III collagen (C3M), neo-epitope of MMP-2 mediated degradation of type VI collagen (C6M).

A by-subject listing of biomarkers including observed values, absolute and percent change from baseline will be provided.

Additional exploratory biomarker analyses, if deemed necessary, will be reported in a separate report.

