8.2.4 Change from Baseline

Change from baseline is calculated as:

- Visit value – baseline value.

Percentage change from baseline is calculated as:

- (Change from baseline / baseline value) * 100.

The percent of baseline is calculated as:

- (Visit value / baseline value) * 100.

If either the baseline or visit value is missing, the change and percent change from baseline is missing.

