13.1 Pharmacodynamic Analyses

The absolute change from baseline in FXIIa-mediated kallikrein activity over time will be calculated for each subject. The comparison of primary interest is the change from baseline at Day 92 (Week 14). The change from baseline will be compared between CSL312 and placebo using a mixed-model repeated measure (MMRM) analysis, with treatment group and visit as fixed effects, and baseline as a covariate. Interactions with visit will be included for treatment group and baseline. The analysis will be implemented by using SAS PROC MIXED. A restricted maximum likelihood (REML) approach will be used. An unstructured variance-covariance structure will be used to model the within-subject errors. This variance-covariance matrix will be estimated across treatment groups. If the model fails to converge, a heterogeneous Toeplitz structure (the TOEPH option in SAS PROC MIXED) will be used. The Kenward-Roger approximation will be used to estimate denominator degrees of freedom and adjust standard errors. Mean difference in least square means (LSMeans) between treatment groups and its 95% confidence interval will be provided at each time point, assuming that the data is normally distributed. If the data are not normally distributed by visual inspection of residual plots (QQ plots), an appropriate data transformation, log transformation, may be done.

FXIIa-mediated kallikrein activity will be summarized by nominal time point with the following descriptive statistics: n, mean, SD, %CV, minimum, Q1, median, Q3, maximum, geometric mean, geometric %CV, and percent below the limit of quantification (% BLQ).

Individual observed FXIIa-mediated kallikrein activity-time profiles will be plotted using actual sampling times. Mean (\pm SD) observed FXIIa-mediated kallikrein activity-time profiles will be plotted by using nominal (planned) time points.

The absolute change from baseline, percent change from baseline, and percent of baseline of FXIIa-mediated kallikrein activity over time will be summarized using descriptive statistics as done for the observed values of FXIIa-mediated kallikrein activity. The absolute change from baseline and percent of baseline of FXIIa-mediated kallikrein activity will also be presented graphically by treatment group as done for the observed FXIIa-mediated kallikrein activity.

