Other observed PD parameter of FXII concentration will be summarized by nominal time point by descriptive statistics (n, mean, SD, %CV, minimum, Q1, median, Q3, maximum, geometric mean, geometric %CV). The absolute and percent change from baseline for those PD parameters will also be summarized by nominal time point by descriptive statistics. For all PD parameters, including aPTT, the absolute changes from baseline will be analyzed by the MMRM as described for FXIIa-mediated kallikrein activity.

Individual observed PD parameter time profiles will be plotted using actual sampling times. Mean (\pm SD) observed PD parameter time profiles will be plotted by using nominal (planned) time points.

A by-subject listing of PD parameters including observed values, absolute and percent change from baseline will be provided.

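### SAP 13.1 and 13.2 specify geometric mean, geometric %CV and %CV for absolute and percent change from baseline, quantities that can be negative, and give no rule for non-positive values

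*SAP*

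**What the plan says.** SAP 13.2 puts three quantities under one instruction: "For biomarkers the observed values, the absolute and percent change from baseline will be summarized by nominal time point by descriptive statistics". The list in parentheses that follows is "n, mean, SD, %CV, minimum, Q1, median, Q3, maximum, geometric mean, geometric %CV). The MMRM as described for FXIIa-mediated kallikrein activity is also applicable", so geometric mean, geometric %CV and %CV apply to observed values, absolute change and percent change alike.

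SAP 13.1 reaches the same place for FXIIa-mediated kallikrein activity by cross-reference. The list for observed values is "n, mean, SD, %CV, minimum, Q1, median, Q3, maximum, geometric mean, geometric %CV, and percent below the limit of quantification (% BLQ", and absolute change, percent change and percent of baseline "will be summarized using descriptive statistics as done for the observed values of FXIIa-mediated kallikrein activity".

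SAP 8.2.4 defines absolute change as "Visit value – baseline value", percent change as "Change from baseline / baseline value) * 100" and percent of baseline as "Visit value / baseline value) * 100".

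Neither 13.1 nor 13.2 has a rule for zero or negative values: no offset, no instruction to leave the cell uncalculated, no move to a ratio scale. The imputation rules in SAP 12.1 cover CSL312 plasma concentrations only.

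**The concern.** A geometric mean is exp(mean(log x)) and exists only if every x is positive. A change from baseline is negative for each subject whose marker falls, so as soon as one subject declines there is no valid geometric mean or geometric %CV of the changes for the whole group. The ordinary %CV (SD divided by mean) has a separate problem: it becomes arbitrarily large or changes sign as the mean change approaches zero, which is where a stable placebo group should lie.

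The risk is a misleading entry in the PD and biomarker tables. If the program takes logs and non-positive values become missing, a group with no change, or even a group that declines, would show a positive geometric mean change resting on an unreported subset. Protocol 1.3 describes the study as establishing proof of mechanism, so readers will look at these tables for the direction of effect.

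**Working it through.** The plan states no figure on this point, so there is none to reproduce.

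**1. Sign of the quantities.** Let R = visit/baseline, with baseline positive. By SAP 8.2.4, percent change = 100(R − 1), which is negative when R < 1, and absolute change has the same sign. Percent of baseline = 100R, which is positive whenever the visit value is positive. The log is therefore defined for percent of baseline but not for either change.

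**2. Chance that the statistic is valid.** SAP 4.4 plans 35 evaluable subjects per arm. If each is equally likely to rise or fall, the chance that all 35 changes are positive is 0.5^35, about 3 × 10⁻¹¹.

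**3. What would print if non-positive values went missing, with no true mean change.** The documents give no biomarker variability, so the CVs are assumptions. Take R log-normal with mean 1 and coefficient of variation CV. Then σ = √ln(1 + CV²), the log-mean is −σ²/2, the share dropped is P(R ≤ 1) = Φ(σ/2), and the printed value is exp(E[log 100(R − 1) | R > 1]), obtained numerically.

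| Assumed CV of R | σ | Share dropped, Φ(σ/2) | Risers-only geometric mean percent change |
|---|---|---|---|
| 15% | 0.149 | 53% | +8% |
| 30% | 0.294 | 56% | +16% |
| 50% | 0.472 | 59% | +26% |

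These figures depend on how the CV is read. If 15%, 30% and 50% are within-subject CVs acting independently at both visits, log R has mean 0 and SD √2·σ. Half the subjects are then dropped and the values are about +12%, +26% and +47%.

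**4. What would print with a true decline.** Simulated arms of 35, assuming a log-SD of R of 0.4:

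| Median R | Mean number with a rise | Arithmetic mean percent change | Risers-only geometric mean percent change | Geometric mean of R, minus 1 |
|---|---|---|---|---|
| 0.8 | 10.1 of 35 | −13% | +19% | −20% |
| 0.6 | 3.5 of 35 | −35% | +16% | −40% |
| 0.1 | 0.0 of 35 | −89% | not calculable | −90% |

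At median R = 0.8, the risers-only value runs from +8% to +35% as the assumed log-SD goes from 0.2 to 0.6. It is positive by construction. The last column uses all 35 subjects and recovers the assumed median ratio.

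**5. Kallikrein activity on CSL312.** Protocol 3.3.2 projects median inhibition of at least 90% at the nadir of the SC dosing interval. That is close to the R = 0.1 row, so this arm's geometric cells for change would probably be empty.

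**6. Comparison within the SAP.** SAP 13.2.1 summarizes observed FVC and its absolute change with n, mean, SD, minimum, Q1, median, Q3 and maximum: no geometric statistics and no %CV.

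**The case against.** The strongest reply is that nothing inferential depends on these cells. In Protocol 2.2.2 and 2.3.2 the PD and biomarker summary measures are mean (SD) change, mean percentage of baseline (kallikrein activity) and mean percent change (PD and biomarkers); none is geometric. The between-group comparison is the MMRM on absolute change. The same tables print the mean, median and quartiles, so a positive geometric mean beside a median near zero could be noticed. All of this stands and limits the point to descriptive output.

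Three stronger readings are tempting, and the documents do not support them.

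- A reader might infer that the tables will certainly show risers-only numbers. The SAP names SAS 9.4 or higher but does not say how non-positive values are treated; a blank or not-calculable cell is equally consistent with the text.
- A reader might infer that the CSL312 kallikrein cell would reflect a few non-responders, giving a wrong result for the secondary PD endpoint. At the projected inhibition essentially no subject would have a positive change, and the endpoint's own measures are untouched. A few-risers value is plausible only for markers with a weaker effect.
- A reader might extend the point to FXII concentration. SAP 13.1 says only: "The absolute and percent change from baseline for those PD parameters will also be summarized by nominal time point by descriptive statistics". It attaches no list to those changes, and SAP 7 supplies a default without geometric statistics unless others are named. FXII changes are therefore not affected.

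**Conclusion.** The specification is wrong as written in two places: SAP 13.2 for the biomarkers and SAP 13.1 for kallikrein activity. Geometric mean and geometric %CV of absolute or percent change have no valid value for a group once any subject's value falls or stays the same, and %CV of a change is unstable when the mean change is near zero. This follows from the SAP's own definitions and needs no assumption.

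The form of the error does depend on programming that the SAP leaves open: an uncalculable cell, or a positive figure for risers only. The sizes shown rest on assumed log-normal variability and, in the no-change case, on how the CV is read. The upward direction does not depend on those choices.

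The primary safety endpoint, the PD and biomarker summary measures, the MMRM, medians and quartiles are unaffected. The point is worth correcting because the statistic is invalid and its removal loses nothing that the protocol requires.

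**What to change.** In SAP 13.1 (kallikrein activity) and 13.2 (biomarkers), limit geometric mean, geometric %CV and %CV to observed values and, for kallikrein activity, percent of baseline, which 13.1 already plans to summarize. For absolute and percent change, list n, mean, SD, minimum, Q1, median, Q3 and maximum, as in SAP 13.2.1.

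If a geometric summary of relative change is wanted for the biomarkers, add percent of baseline as defined in SAP 8.2.4. Section 13.2 does not plan it now, so this would be an optional addition. No change is needed for FXII concentration.

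The cost is an edit to SAP wording and table shells before database lock. It needs no new data and leaves the endpoints and models as they are.

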8.1.4 Biomarker Assessments

The proposed mechanism of action of CSL312 in IPF will be explored using biomarkers of coagulation, inflammation, alveolar epithelial cell damage, tissue modeling, and fibrosis, such as but not limited to, those detailed below.

The following biomarkers will be measured: pF1+2, fibrinogen, D-dimer, aPTT, high-sensitivity C-reactive protein (hs-CRP), and monocytes. Samples will be collected at Screening, before administration of the IV loading dose of investigational product on Day 1, and on Days 8, 36, 64 and 92. hs-CRP will be assessed at all study visits, including Screening, before administration of the IV loading dose investigational product and immediately after the EOI on Day 1.

The following biomarkers will be measured at Screening, before administration of the IV loading dose of investigational product on Day 1, and on Days 8, 36, 64, and 92: FXII (free vs. total), C3a, C5a, IL-8, IL-10, CCL-2, CXCL-1, CCL-18, PAI-1, surfactant protein A (SP-A), surfactant protein D (SP-D), YKL-40, tenascin-C (TN-C), thrombospondin-1 (TSP-1), VEGF, neo-epitope of matrix metalloproteinase-mediated degradation of citrullinated vimentin (VICM), neo-epitope of matrix metalloproteinase-mediated degradation of C-reactive protein (CRPM), pro-Fib, neo-epitope of calprotectin generated by human neutrophil elastase (CPa9-HNE), and collagen synthetic and degradation neo-epitopes (pro-C3/4/6 and C1/3/4/6M).

The following PD parameters and biomarkers will be assessed at all study visits at which PK is being assessed, including before administration of the IV loading dose of investigational product and immediately after the EOI on Day 1: FXIIa-mediated kallikrein activity, FXII concentration, IL-6, and hs-CRP. Additionally, hs-CRP will also be assessed at Screening.

Blood transcriptomics: Blood will be collected for RNA sequencing to investigate changes in gene expression at Screening, before administration of the IV loading dose of investigational product on Day 1, and on Days 8, 36, 64, and 92.

Proteomic analysis: Blood will be collected to characterize the plasma proteome at Screening, before administration of the IV loading dose of investigational product on Day 1, and on Days 8, 36, 64, and 92.

Details related to the collection, preparation, transfer, and storage of biomarker samples will be provided in the laboratory manual. Blood sampling time points for biomarker assessment are indicated in the [Schedule of Assessments](#).

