10.3.5 Pharmacodynamic Analyses

10.3.5.1 FXIIa-mediated Kallikrein Activity

Change from Baseline in FXIIa-mediated kallikrein activity over time will be calculated for each subject. The comparison of primary interest is the change from Baseline at Week 14. If the data are not normally distributed by visual inspection or statistical testing, an appropriate data transformation may be done. The data (or transformed data) will be compared between CSL312 and placebo using mixed-model repeated measure (MMRM), with treatment group and visit as fixed effects, and Baseline as a covariate. Analyses will be implemented using SAS PROC MIXED. Interactions with visit will be included for treatment group and Baseline. A restricted maximum likelihood (REML) approach will be used. An unstructured variance-covariance structure will be used to model the within-subject errors. This variance-covariance matrix will be estimated across treatment groups. If the model fails to converge, a heterogeneous Toeplitz structure (the TOEPH option in SAS PROC MIXED) will be used. The Kenward-Roger approximation will be used to estimate denominator degrees of freedom and adjust standard errors.

FXIIa-mediated kallikrein activity will be summarized by nominal time point with the following descriptive statistics: n, mean, SD, %CV, minimum, first quartile (Q1), median, third quartile (Q3), maximum, geometric mean, geometric %CV, and percent below the limit of quantitation (%BLQ). Individual FXIIa-mediated kallikrein activity-time profiles will be plotted using actual sampling times. Mean (\pm SD) FXIIa-mediated kallikrein activity profiles will also be plotted using nominal (planned) time points.

Observed change from Baseline and percentage of Baseline values of FXIIa-mediated kallikrein activity over time will also be summarized using descriptive statistics and presented graphically by treatment group.

A nonparametric Jonckheere-Terpstra test may be performed as appropriate to test the trend over time for each treatment group.

The PD Analysis Set will be used for this analysis. Additional information on the analyses of FXIIa-mediated kallikrein activity will be provided in the SAP.

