10.3.7 Analysis of Exploratory Endpoints

10.3.7.1 Biomarker Analyses

All PD and biomarker data change from Baseline and percent change from Baseline in the blood will be analyzed using the same methodologies as described for FXIIa-mediated kallikrein activity (see [Section 10.3.5.1](#)). In addition, correlations between the change from Baseline for each PD and biomarker at Week 14 and each spirometry measurement of FVC (change from Baseline in FVC [mL] and in FVC percent predicted) measured at Week 14 may be investigated using a scatter plot, Pearson correlation coefficient and Spearman correlation coefficient by treatment group. All PD and biomarker data will be summarized and analyzed using the PD Analysis Set. Additional information on PD analyses will be provided in the SAP.

Additional exploratory biomarker analyses will be reported separately from the clinical study report (CSR).

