4.5.1 Independent Data Monitoring Committee

The roles and responsibilities of the independent data monitoring committee (IDMC) and the safety data review schedules are described in the IDMC charter. Operationally, since the IDMC is ad-hoc and can be triggered before SAS programming can be done to generate summary output, in this case, only data dump listings will be generated. Otherwise, those summary tables will be provided for the following (along with their supporting listings):

- Demographics;
- Treatment and exposure;
- AE overall summary, SAEs, AEs, AESIs.

Other safety analysis output as listed below, will be provided as data listings:

- Vital signs, physical exams and respiratory tests;
- Safety laboratory parameters / urinalysis;
- ECG;
- Medical history;
- Concomitant medication;
- Spirometry.

Please refer to [Sections 9, 10, and 11](#) of this SAP for descriptions of the analysis listed above.

5 Changes from the Protocol Planned Analyses

There are no changes to the planned analyses as previously documented in the CSP.

The definition of screened analysis set was slightly modified, please refer to Section 6.1.

6 Study Analysis Sets

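### SAP 13.2 applies the protocol's biomarker analysis to nine of the 32 biomarkers named in Protocol 8.1.4, leaves out IL-6, and Section 5 declares no change

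*SAP*

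**What the plan says.** Protocol 10.3.7.1 sets scope and method together: "All PD and biomarker data change from Baseline and percent change from Baseline in the blood will be analyzed using the same methodologies", namely those set out for kallikrein activity. Protocol 10.3.5.1 gives those methods: change from Baseline is compared between arms "using mixed-model repeated measure (MMRM), with treatment group and visit as fixed effects, and Baseline as a covariate", and descriptive summaries are given by time point. Section 10.3.7.1 then adds, without a condition, "Additional exploratory biomarker analyses will be reported separately from the clinical study report (CSR").

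Protocol 8.1.4 names the markers. One group is to be measured at every visit with PK sampling: "FXIIa-mediated kallikrein activity, FXII concentration, IL-6, and hs-CRP".

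SAP 13.2 says "The MMRM as described for FXIIa-mediated kallikrein activity is also applicable for all biomarkers and aPTT (absolute change from baseline for each"), and then lists what it means by biomarker: CCL-18, PAI-1, SP-A, SP-D, YKL-40, PROC3, PROC6, C3M and C6M. SAP 13.2.1 repeats the same nine for each series of scatter plots against FVC, so the list is not illustrative. IL-6 appears nowhere in the supplied SAP text. SAP 13.2 ends with "Additional exploratory biomarker analyses, if deemed necessary, will be reported in a separate report".

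SAP Section 5 states "There are no changes to the planned analyses as previously documented in the CSP" and flags only a revised definition of the Screened Analysis Set.

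**The concern.** Protocol 1.3 gives the overall aim as proof of mechanism in support of further development decisions, and the biomarkers carry much of that evidence. Protocol 1.2.2 reports that CSL312 inhibited five mediators in lung fibroblasts: CXCL-1, MCP-1 (CCL-2), IL-6, IL-8 and PAI-1. Only PAI-1 is on the SAP list. IL-6 also appears in the design rationale in Protocol 3.3.1.

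Under the SAP as written, whether any further biomarker report is produced is a later judgement, with no criterion and no timing. That judgement could be made with results in hand. There is no multiplicity control, so a reader needs the full set of markers to weigh the nominally significant ones. A reader who relies on Section 5 would not learn that the set had been cut.

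**Working it through.** The documents give no marker count of their own, so the check is a count and a comparison.

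**1. Variables named in Protocol 8.1.4**
- Coagulation and inflammation group: pF1+2, fibrinogen, D-dimer, aPTT, hs-CRP, monocytes = 6.
- Second group: FXII free vs. total (counted once), C3a, C5a, IL-8, IL-10, CCL-2, CXCL-1, CCL-18, PAI-1, SP-A, SP-D, YKL-40, TN-C, TSP-1, VEGF, VICM, CRPM, Pro-Fib, CPa9-HNE = 19. Collagen neo-epitopes pro-C3, pro-C4, pro-C6, C1M, C3M, C4M, C6M = 7. Together 19 + 7 = 26.
- PK-visit group: kallikrein activity, FXII concentration, IL-6, hs-CRP = 4.
- Total: 6 + 26 + 4 = 36. hs-CRP appears twice, so 36 − 1 = 35 distinct variables.

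RNA sequencing and proteomics are not counted, because they are not single markers.

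**2. Split into PD parameters and biomarkers**

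Protocol 8.1.3, Table 8, names three PD parameters: kallikrein activity, FXII concentration and aPTT. That leaves 35 − 3 = 32 biomarkers.

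**3. What the SAP models**

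SAP 13.1 and 13.2 apply the MMRM to the three PD parameters and the nine listed biomarkers. All nine are among the 32.
- All variables: 3 + 9 = 12 of 35 (34%).
- Biomarkers: 9 of 32 (28%).
- Biomarkers without a between-arm model: 32 − 9 = 23 (72%).

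**4. What the 23 still receive**

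SAP 11.3 summarizes pF1+2, fibrinogen, D-dimer, hs-CRP and monocytes by visit and treatment group as safety laboratory tests. The rest, 23 − 5 = 18, have no planned analysis in the SAP: IL-6, IL-8, IL-10, CCL-2, CXCL-1, C3a, C5a, FXII free vs. total, TN-C, TSP-1, VEGF, VICM, CRPM, Pro-Fib, CPa9-HNE, pro-C4, C1M and C4M.

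**5. Sensitivity of the count**

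The documents do not settle whether FXII free vs. total is distinct from the modelled FXII concentration. If it is the same measurement, the figures become 31 biomarkers, 22 without a model and 17 without any planned analysis.

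**6. In vitro targets**

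Of the five mediators in Protocol 1.2.2, one (PAI-1) is listed, so 5 − 1 = 4 have no planned analysis.

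**7. Reporting clause**

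The protocol first commits to analyzing all the markers and then says that additional analyses will be reported outside the CSR. The SAP makes that report conditional. It also does not say that the unlisted markers would be in it.

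**The case against.** **These are exploratory endpoints.** Protocol 10.3.1 calls all p-values nominal, and SAP 4.1.1 states that there is no primary hypothesis. This stands, and it rules out any complaint about error rates. It does not excuse declaring no change.

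**The protocol allows separate reporting.** It does, but only for additional analyses, after the commitment covering all markers and without a condition.

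**The nine were fixed early.** The SAP is dated 28 April 2022, and Protocol 6.3.1 keeps central-laboratory samples blinded until database lock. Nothing suggests that the nine were picked from results. The risk lies in the unlisted remainder.

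**Version lag.** The SAP rests on the protocol through Amendment 2, whose text is not supplied; the protocol reviewed is Amendment 3. The Amendment 3 change list touches 8.1.4 only on where PT and INR are measured and names no change to the biomarker analysis. Lag is therefore unlikely, though it cannot be excluded.

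Two stronger readings are tempting, and the documents do not support either:
- *A required MMRM on percent change has been dropped.* Protocol 10.3.7.1 can be read that way. But the section it points to models change from Baseline and only summarizes percentage of Baseline. The exploratory endpoint table in Protocol 2.3.2 likewise asks for mean percent change by treatment. The SAP's approach, a model for absolute change and descriptives for percent change, fits that narrower reading.
- *Coagulation and inflammation have no pre-specified analysis.* Kallikrein activity, FXII concentration, aPTT, PAI-1 and CCL-18 are all modelled, and five further markers have laboratory descriptives. Coverage is narrowed, not absent.

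**Conclusion.** The point holds as an undeclared narrowing of the biomarker analysis. On the current protocol text, 23 of 32 named biomarkers (22 of 31 if the FXII measures overlap) have no between-arm model, and about 18 (or 17) have no planned analysis at all. IL-6 and three other in vitro targets of the drug are among them. Section 5 does not mention this, and the only route to a further report is conditional.

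The conclusion assumes that the 8.1.4 marker list and the 10.3.7.1 commitment read the same in Amendment 2. It does not depend on how the percent-change wording is read. The consequence is a gap in the record and a selective-reporting risk for the remainder of the panel. It should be corrected before database lock.

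**What to change.** Do one of the following before database lock:
- Restore the omitted Protocol 8.1.4 markers to the SAP 13.2 list under the existing model, at least IL-6, IL-8, CCL-2 and CXCL-1.
- List in SAP Section 5 which markers are removed from the protocol's analysis, why, and where each will be reported.

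If only some are restored, declare the rest in Section 5. In every case:
- Remove the condition on the separate report in SAP 13.2, and say that the remaining markers will be reported whatever the results show.
- State in Section 5 that percent change is summarized descriptively only, because the protocol sentence can be read as requiring more.

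Declaring the removal costs a paragraph. Restoring markers costs more runs of a model already specified, a longer table set and up to 23 more sets of nominal p-values. Neither needs a change to the design or to data collection.
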